**Table 7: Temozolomide Dose Levels for Maintenance Treatment**

Dose Level	Dose (mg/m  /day)	Remarks
-1	100	Reduction for prior toxicity
0	150	Dose during Cycle 1
1	200	Dose during Cycles 2-6 in absence of toxicity

**Table 8: Temozolomide Dose Reduction or Discontinuation During Maintenance Treatment**

Toxicity	Reduce TMZ by 1 Dose Level a	Discontinue TMZ
Absolute Neutrophil Count	<1.0 x 10  /L	See footnote b
Platelet Count	<50 x 10  /L	See footnote b
CTC Non-hematological Toxicity (except for alopecia, nausea, vomiting)	CTC Grade 3	CTC Grade 4 b

TMZ = temozolomide; CTC = Common Toxicity Criteria

a TMZ dose levels are listed in [Table 7](#).

b TMZ is to be discontinued if dose reduction to <300 mg/m^2 is required or if the same Grade 3 nonhematological toxicity (except for alopecia, nausea, vomiting) recurs after dose reduction.

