## 16.2 Post-Radiation Temozolomide

Patients will receive up to 12 cycles of adjuvant temozolomide at a dose of 150-200 mg/m^2 Days 1-5 of a 28-day cycle and along with PLX3397. Temozolomide will be administered orally once per day for 5 consecutive days (Days 1-5) of a 28-day cycle. The starting dose for the first cycle will be 150 mg/m^2/day, with a single dose escalation to 200 mg/m^2/day in subsequent cycles if no treatment-related adverse events >Grade 2 are noted.

The start of the first cycle will be scheduled 28 days ± 7 days after the last day of radiotherapy. The start of all subsequent cycles (2-12) will be scheduled every 4 weeks (28 days ± 7 days) after the first daily dose of temozolomide of the preceding cycle.

The dose will be determined using the BSA calculated at the beginning of each treatment cycle. The BSA will be calculated from the height obtained at the pretreatment visit and from the weight obtained at the visit immediately before each cycle. Capsules of temozolomide are available in 5, 20, 100, 140, 180, and 250 mg. The daily dose will be rounded to the nearest 5 mg. If the investigator does not want to prescribe the temozolomide 5 mg unit strength, he/she should round off the dose to the closest 10 mg. For example for a 1.7 m^2 subject, the 75 mg/m^2 dose would be 127.5 mg and the dose would be rounded off to 120 mg. For the same subject, the 150 mg/m^2 dose would be 255 mg and the dose would be rounded off to 260 mg. The exact dose administered should be recorded in the CRF. Each daily dose should be given with the least number of capsules.

Patients will be instructed to fast at least 2 hours before and 1 hour after temozolomide administration. Water is allowed during the fast period. Patients will be instructed to swallow the capsules whole, in rapid succession, without chewing them. Treatment should be given at night.

If vomiting occurs during the course of treatment, no re-dosing of the patient is allowed before the next scheduled dose.

Antiemetic prophylaxis with a 5-HT3 antagonist is strongly recommended and should be administered 30 to 60 minutes before temozolomide administration.

Dose reductions of temozolomide during the adjuvant period should be made according to the prescribing information, as summarized below.

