**TABLE 2: Temozolomide Dose Levels for Maintenance Treatment**

Dose Level	Dose (mg/m  /day)	Remarks
-1	100	Reduction for prior toxicity
0	150	Dose during Cycle 1
1	200	Dose during Cycles 2-6 in absence of toxicity

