**TABLE 3: Temozolomide Dose Reduction or Discontinuation During Maintenance Treatment**

Toxicity	Reduce TMZ by 1 Dose Level*	Discontinue TMZ
Absolute Neutrophil Count	less than $1.0 \times 10^9/L$	See footnote†
Platelet Count	less than $50 \times 10^9/L$	See footnote†
CTC Nonhematological Toxicity (except for alopecia, nausea, vomiting)	CTC Grade 3	CTC Grade 4†

[figure not shown]
\*TMZ dose levels are listed in Table 2.

†TMZ is to be discontinued if dose reduction to less than 100 mg/m^2 is required or if the same Grade 3 nonhematological toxicity (except for alopecia, nausea, vomiting) recurs after dose reduction.

TMZ=temozolomide; CTC=Common Toxicity Criteria.

**Patients with Refractory Anaplastic Astrocytoma:** For adults the initial dose is 150 mg/m^2 once daily for 5 consecutive days per 28-day treatment cycle. For adult patients, if both the nadir and day of dosing (Day 29, Day 1 of next cycle) ANC are greater than or equal to  $1.5 \times 10^9/L$  (1500/ $\mu$ L) and both the nadir and Day 29, Day 1 of next cycle platelet counts are greater than or equal to  $100 \times 10^9/L$  (100,000/ $\mu$ L), the TEMODAR dose may be increased to 200 mg/m^2/day for 5 consecutive days per 28-day treatment cycle. During treatment, a complete blood count should be obtained on Day 22 (21 days after the first dose) or within 48 hours of that day, and weekly until the ANC is above  $1.5 \times 10^9/L$  (1500/ $\mu$ L) and the platelet count exceeds  $100 \times 10^9/L$  (100,000/ $\mu$ L). The next cycle of TEMODAR should not be started until the ANC and platelet count exceed these levels. If the ANC falls to less than  $1.0 \times 10^9/L$  (1000/ $\mu$ L) or the platelet count is less than  $50 \times 10^9/L$  (50,000/ $\mu$ L) during any cycle, the next cycle should be reduced by 50 mg/m^2, but not below 100 mg/m^2, the lowest recommended dose (see Table 4). TEMODAR therapy can be continued until disease progression. In the clinical trial, treatment could be continued for a maximum of 2 years, but the optimum duration of therapy is not known.

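### Table 8 footnote b stops temozolomide at a reduction below 300 mg/m², above every adjuvant dose the protocol allows; the label it summarizes says below 100

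*Combined protocol and SAP*

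**What the plan says.** Section 16.2 names the source of the adjuvant rule: "Dose reductions of temozolomide during the adjuvant period should be made according to the prescribing information, as summarized below". Adjuvant dosing starts at 150 mg/m²/day, "with a single dose escalation to 200 mg/m"²/day. Table 7 then gives three levels in mg/m²/day: level −1 at 100, labelled "Reduction for prior toxicity"; level 0 at 150; and level 1 at 200.

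Table 8 has a column headed "Reduce TMZ by 1 Dose Level", triggered by low neutrophils, low platelets or Grade 3 non-hematological toxicity. Its footnote a refers the reader to Table 7 for the levels. In the discontinuation column, the neutrophil and platelet rows contain only a pointer to footnote b, which begins "TMZ is to be discontinued if dose reduction to <300 mg/m"² is required. It continues "or if the same Grade 3 nonhematological toxicity (except for alopecia, nausea, vomiting) recurs after dose reduction".

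The label in Attachment 4 carries the same pair of tables. Its dose levels are in "TABLE 2: Temozolomide Dose Levels for Maintenance Treatment", and the footnote to its Table 3 begins "TMZ is to be discontinued if dose reduction to less than 100 mg/m"² is required.

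**The concern.** A stopping threshold for dose reduction only works if it lies at or just below the lowest usable dose. This one lies above the highest. Taken per day, any reduction at all is a reduction to less than 300 mg/m², so the patient stops temozolomide at the first event for which the label would lower the dose and continue.

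Three other parts of the protocol would then have no function: level −1 in Table 7, the one-level reduction column in Table 8, and the second half of footnote b, which presupposes that a dose reduction has already taken place. Because the neutrophil and platelet rows rely wholly on footnote b, it is also the only hematologic discontinuation rule in the table.

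At stake is who stays on backbone temozolomide after maintenance-phase toxicity.

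**Working it through.** No sample-size or error-rate formula is involved. The check compares the two sets of tables and then runs the threshold through the dose levels.

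**1. Comparison with the stated source**

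| Item | Protocol Tables 7 and 8 | Label Tables 2 and 3 (Attachment 4) | Agree? |
|---|---|---|---|
| Level −1 (mg/m²/day) | 100 | 100 | yes |
| Level 0 (mg/m²/day) | 150 | 150 | yes |
| Level 1 (mg/m²/day) | 200 | 200 | yes |
| Neutrophils, reduce (×10⁹/L) | <1.0 | <1.0 | yes |
| Platelets, reduce (×10⁹/L) | <50 | <50 | yes |
| Non-hematological, reduce | Grade 3 | Grade 3 | yes |
| Non-hematological, discontinue | Grade 4 | Grade 4 | yes |
| Same Grade 3 toxicity after a reduction | discontinue | discontinue | yes |
| Reduction threshold for discontinuation (mg/m²) | <300 | <100 | **no** |

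Eight of nine items agree. The figure 300 cannot be obtained from the source that Section 16.2 names.

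**2. Per-day reading**

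Footnote a points to Table 7, which is per day, so this is the natural reading. The rule is: discontinue if the reduced dose is below the threshold. The listed levels are 50 apart. The step below 100 is not listed; I take it as 50 by the same spacing.

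| Current dose | Reduced dose | Below 300? | Below 100? |
|---|---|---|---|
| 200 | 150 | yes, stop | no, reduce |
| 150 | 100 | yes, stop | no, reduce |
| 100 | 50 | yes, stop | yes, stop |

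Of the two reductions that Table 7 actually lists, 2 of 2 become discontinuations at 300 and 0 of 2 at 100.

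Table 8 has three reduction triggers, and the threshold acts identically on each:

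- At 300: 3 levels × 3 triggers = 9 of 9 cells discontinue.
- At 100: 1 level × 3 triggers = 3 of 9 cells discontinue.
- Difference: 9 − 3 = 6 of 9 cells change from reduce to discontinue.

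**3. Five-day-total reading**

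Temozolomide is given on 5 days of each 28-day cycle, so the figure might be meant as a cycle total.

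- 300 / 5 = 60 mg/m²/day, which is not a Table 7 level.
- The levels as cycle totals are 5 × 200 = 1000, 5 × 150 = 750 and 5 × 100 = 500 mg/m².
- The label floor as a cycle total is 5 × 100 = 500, not 300.
- The listed reductions give 750 and 500, neither below 300, so both are allowed. A further step to 50/day gives 5 × 50 = 250, which is below 300 and stops treatment.

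On this reading the decisions at the listed levels match the label, but the number does not, and the reader has to supply a unit that the footnote omits. The label states the unit when it does use five-day totals (Attachment 4, section 10, Overdosage).

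**4. With the threshold at <100 mg/m²/day**

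Reductions from 200 to 150 and from 150 to 100 are allowed, and discontinuation applies only when a dose below level −1 would be needed. This fits Table 7, the reduction column of Table 8 and the label footnote. The label's anaplastic astrocytoma paragraph (section 2.1) also treats 100 mg/m² as the lowest recommended dose.

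**The case against.** The strongest case against accepts the mismatch and disputes how much it matters.

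- **It may be a misread digit.** The point rests on a 3 where a 1 belongs, in text extracted from a PDF, and the extraction is imperfect elsewhere: the QTcF formula is rendered differently in the two flow charts. The footnote appears once in the protocol body, so the documents cannot settle this. The caveat stands and calls for a look at the source file. As the text reads, however, the figure is 300.
- **The right rule is in the document already.** Sections 13.14.1, 13.14.2 and 16.2 send temozolomide reductions to the label. Section 13.14.1 requires consultation with the Medical Monitor for adjuvant-period reductions. Section 13.14.2 does the same for all adjustments and describes its parameters as guidance that does not override clinical judgment. This does reduce the risk. But Section 13.14.2 also names Section 16 as a summary of the label, so sites are told that the two are equivalent when they are not.
- **The harmful reading defeats itself.** A threshold above every permitted dose is conspicuous and contradicts the reduction column in the same row, so a site is likely to query it. A plausible wrong value such as 150 would be more dangerous. This also stands, and it limits the severity.
- **The cell count overstates the effect.** The plain content is two listed reductions; multiplying by three identical triggers and adding an unlisted step to 50 gives 9. The cells carry no frequency weight. That is fair, and the counts should be read only as a description of the table.
- **The label footnote does not say per day.** Correct. Adding the unit is a clarification drawn from Table 7 and label Table 2, not a literal match.

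Nothing in the documents supports 300 as an intended value.

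**Conclusion.** The concern holds. The threshold in Table 8 footnote b contradicts Table 7 and the label that Section 16.2 says it summarizes. On the per-day reading it converts both listed reductions into discontinuations, or 6 of 9 trigger-by-level cells from reduce to discontinue. On an unstated five-day-total reading the decisions at the listed levels would match the label, although the figure would still not correspond to the label's floor.

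The conclusion assumes that the extracted digit is what the source PDF shows. The 9-cell count also assumes a 50 mg/m² step below level −1; the count for the two listed reductions does not. No patient-level effect can be calculated, because the documents give no rate of maintenance-phase dose reduction.

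This is a definite error in a treatment-stopping rule with limited practical risk. It should be fixed, but it does not affect sample size, alpha, power or the planned analysis.

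**What to change.** Check the digit against the source PDF. In Table 8 footnote b, replace <300 mg/m² with <100 mg/m²/day. The value then matches the footnote to label Table 3 in Attachment 4, and the unit matches Table 7. Leave the rest of the footnote as it is.

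The cost is one figure and its unit in one footnote, plus a short memo to sites. No other table and no part of the statistical section needs to change.

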### 16.3 Temozolomide Prescribing Information

Full temozolomide prescribing information is located in [Attachment 4](#). Key features are highlighted below.

#### 16.3.1 Storage and Stability

The capsules are packaged in amber glass bottles and should be stored at 25°C. Temperature excursions between 15 and 30°C are permissible. Refer to the commercially labeled bottles for expiration dating.

### 16.3.2 Pharmacokinetics

Temozolomide is rapidly and completely absorbed after oral administration; peak plasma concentrations occur in 1 hour. Food reduces the rate and extent of temozolomide absorption. Mean peak plasma concentration and AUC decreased by 32% and 9%, respectively, and  $T_{max}$  increased 2-fold (from 1.1 to 2.25 hours) when temozolomide was administered after a modified high-fat breakfast.

Temozolomide is rapidly eliminated with a mean elimination half-life of 1.8 hours and exhibits linear kinetics over the therapeutic dosing range. Temozolomide has a mean apparent volume of distribution of 0.4 L/kg (%CV=13%). It is weakly bound to human plasma proteins; the mean percent bound of drug-related total radioactivity is 15%.

### 16.3.3 Metabolism and Elimination

Temozolomide is spontaneously hydrolyzed at physiologic pH to the active species, 3-methyl-(triazen-1-yl)imidazole-4-carboxamide (MTIC) and to temozolomide acid metabolite. MTIC is further hydrolyzed to 5-amino-imidazole-4-carboxamide (AIC), which is known to be an intermediate in purine and nucleic acid biosynthesis and to methylhydrazine, which is believed to be the active alkylating species. Cytochrome P450 enzymes play only a minor role in the metabolism of temozolomide and MTIC.

### 16.3.4 Special Populations

#### Creatinine Clearance

Caution should be exercised when temozolomide is administered to patients with severe renal impairment. Temozolomide has not been studied in patients on dialysis.

#### Hepatically Impaired Patients

In a pharmacokinetic study, the pharmacokinetics of temozolomide in patients with mild to moderate hepatic impairment (Child's-Pugh Class I-II) were similar to those observed in patients with normal hepatic function. Caution should be exercised when temozolomide is administered to patients with severe hepatic impairment.

#### Gender

Population pharmacokinetic analysis indicates that women have an approximately 5% lower clearance (adjusted for body surface area) for temozolomide than men. Women have higher incidences of Grade 4 neutropenia and thrombocytopenia in the first cycle of therapy than men.

#### Age

Population pharmacokinetic analysis indicates that age (range 19-78 years) has no influence on the pharmacokinetics of temozolomide.

### 16.3.5 Drug-Drug Interactions

In a multiple dose study, administration of temozolomide with ranitidine did not change the  $C_{max}$  or AUC values for temozolomide or MTIC. Population analysis indicates that administration of valproic acid decreases the clearance of temozolomide by about 5%. The clinical implication of this effect is not known. Population analysis failed to demonstrate any influence of co-administered dexamethasone, prochlorperazine, phenytoin, carbamazepine, ondansetron, H2-receptor antagonists, or phenobarbital on the clearance of orally administered temozolomide.

### 16.3.6 Adverse Events

- Hematologic: Thrombocytopenia, leukopenia, myelodysplastic syndrome
- Gastrointestinal: Nausea, vomiting, anorexia
- Hepatic: Elevated liver enzymes (reversible). Additional information regarding hepatic toxicity can be found in [Attachment 4](#).
- Skin: Rash
- Neurologic: Convulsions, weakness on one side of the body, abnormal coordination, paralysis
- Other: Constipation, diarrhea, stomatitis, fatigue, decreased performance status, headache

### 16.3.7 Special Handling and Precautions

Capsules should not be opened or damaged. Rigorous precautions should be taken to avoid capsule contents having contact with skin or mucous membranes. Capsule contents may be irritating to skin and eyes. Mutagenic and prolonged exposure may cause serious health effects (outside of prescribed dosage in this trial).

Temozolomide is potentially mutagenic and should be handled with appropriate precautions by both staff and patients. Capsules should not be opened. If capsules are accidentally opened or damaged, rigorous precautions should be taken with the capsule contents to avoid inhalation or contact with the skin or mucous membranes. Procedures for proper handling and disposal of anticancer drugs should be considered.

### 16.3.8 Contraindications

Temozolomide is contraindicated in patients who have a history of a hypersensitivity reaction to any of its components or to DTIC.

### 16.3.9 Pregnancy Category D

Temozolomide may cause fetal harm when administered to a pregnant woman. There are no adequate and well-controlled studies in pregnant women. If this drug is used during pregnancy, or if the patient becomes pregnant while taking this drug, the patient should be apprised of the

potential hazard to the fetus. **Women of childbearing potential should be advised to avoid becoming pregnant during therapy with temozolomide.**

Treatment of a man with temozolomide may increase the risk of birth defects if he causes a woman to become pregnant while he is taking temozolomide. Men treated with temozolomide may have difficulty causing a woman to become pregnant after their treatment is completed. Men receiving temozolomide should be directed to use effective contraception while they are being treated. There is insufficient data to know what the risk of subsequent problems with fertility will be. Similarly, women who are treated with temozolomide may have difficulty becoming pregnant in the future and may at be at increased risk of having children with birth defects. There is insufficient evidence to determine what the risk of these complications will be.

### **16.3.10 Supply**

Commercially available.

## **17.0 MEASURES TO MINIMIZE/AVOID BIAS**

Each patient will be assigned a unique number and will keep this number for the duration of the study. Patient numbers will not be reassigned or reused for any reason. Patients should be identified to the Sponsor only by their assigned number, initials, date of birth, and sex. The investigator must maintain a patient master log.

## **18.0 SAFETY EVALUATION**

Routine safety and tolerability will be evaluated from the results of reported signs and symptoms, scheduled physical examinations, vital sign measurements, 12-lead ECGs (including QTcF intervals), and clinical laboratory test results.

More frequent safety evaluations may be performed if clinically indicated or at the discretion of the investigator. All AEs will be recorded from the time the patient receives the first dose of study drug up to 28 days after the last dose.

As this is an open label study, ongoing safety will be continuously and rigorously monitored by the Sponsor. Additionally, biweekly teleconferences are planned to review in detail the safety across all study sites.

### **18.1 Physical Examination**

Complete and symptom-directed physical examinations (including neurological exam) will be performed by a licensed physician (or physician's assistant or nurse practitioner).

### **18.2 Vital Signs**

Vital signs (blood pressure, respiratory rate, pulse rate and temperature) will be obtained in the sitting position. Patients should be sitting for 3-5 minutes prior to obtaining vital signs.

### 18.3 Electrocardiograms

Patients should rest in the supine position for at least 5 minutes before each 12-lead ECG recording is started. The ECGs should be reviewed, signed, and dated by a qualified physician (or qualified physician's assistant or nurse practitioner) and any clinically important finding recorded on the appropriate eCRF. The investigator is responsible for providing the interpretation of all ECGs. The results will include heart rate, respiratory rate (RR), PR interval, QRS interval, QT interval, and QTcF interval. Fridericia's formula is required.:

$$QTcF = (QT)^3\sqrt{(RR)}$$

### 18.4 Safety Laboratory Determinations

Laboratory evaluations will be performed as noted in the flow chart. Please see [Attachment 1](#) for the specific laboratory tests to be performed.

## 19.0 BIOMARKER SAMPLES

Blood samples for PD biomarkers will be obtained as noted in the flow chart. Samples will be collected and processed by LabCorp according to the study-specific laboratory manual. LabCorp will perform the MGMT analyses. For all patients, archival tumor samples will be obtained. Please see [Attachment 1](#) for the specific laboratory tests to be performed on both plasma and tissue samples.

## 20.0 PHARMACOKINETIC EVALUATION

### 20.1 Blood Collection

For each PK sample, blood should be collected as noted in the flow chart. Samples will be collected, processed, stored, and shipped according to the study-specific laboratory manual.

Blood samples for PK analysis should be collected at the requested time but within a  $\pm 15$  minute window. The exact actual time of collection should be noted in the source documents and eCRFs.

The total amount of blood to be collected from each patient is <30 mL during screening, <60 mL during Cycle 1, and <30 mL for subsequent cycles.

### 20.2 Bioanalytical Methodology

The plasma and tissue samples will be analyzed for PLX3397 by using a validated method (high performance liquid chromatography (HPLC) with tandem quadrupole mass spectrometric detection) of appropriate specificity and sensitivity.

## **21.0 STATISTICAL ANALYSIS**

### **21.1 General Statistical Considerations**

#### **21.1.1 Phase 1b Portion**

The objective of the Phase 1b portion of this study is to determine the recommended Phase 2 dose (RP2D) of PLX3397 when combined with concurrent radiation therapy and temozolomide. Two expected dose levels are specified for testing, with one or more lower doses to be evaluated if the starting dose of 800 mg/day is above the MTD. For each dose level, 7 patients will be accrued to assure that there will be 6 patients eligible for evaluation of toxicity. A patient registered to the study who is found retrospectively not to meet the study eligibility criteria, who does not receive any PLX3397, or who is considered non-evaluable during the toxicity evaluation period for reasons not related to study drug will be excluded from evaluation of DLT and replaced.

Patient accrual will be suspended after each dose cohort is enrolled until there is sufficient information collected to make a decision relative to dose escalation. A dose level for PLX3397 will be considered acceptable if no more than 2 patients of the 6 eligible patients experience a DLT. Should all 7 patients be analyzable for adverse events, only the first 6 will be considered in the determination of DLTs. If the current level is considered acceptable, then dose escalation will occur and the protocol will be reopened. Otherwise, the preceding acceptable dose level will be declared the MTD. The Sponsor, together with the study investigators, will evaluate the safety of each cohort prior to dose escalation.

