Stopping Rules	
For Phase 1 dose escalation, a dose level will be considered unacceptable if 2 or more patients of the 6 eligible patients experience a DLT (see below). Should all 7 patients in the Cohort be analyzable for adverse events, only the first 6 will be considered in the determination of DLTs. A patient who misses more than 7 days of PLX3397 administration during the 7-week dosing period of Cycle 1 (4 weeks) and Cycle 2 (3 weeks) for reasons other than having had a DLT will be replaced. If 2 or more patients in a Cohort experience a DLT, no patients in the Cohort will be replaced. If >2 of the first 6 patients in Dose Level -2 (400 mg/day of PLX3397) experience a protocol-defined DLT, the combination will be considered too toxic and the study will be discontinued.
 
After approximately 50% of the planned Phase 2 patients have completed their concurrent radiation therapy, an overall interim safety summary will be reviewed by the Medical Monitor and principal investigators to ensure that the potential clinical benefit outweighs the observed clinical risk to date. If the safety observations do not warrant continued enrolment, the study will be discontinued.

PK Parameters	For the Phase 1b portion of the study, a partial AUC ( $AUC_{0-6}$ ) will be calculated using samples collected from C1D8 (pre-temozolomide) and C1D15 (concurrent temozolomide). Values for $C_{max}$ and $T_{max}$ will be determined from the concentration-time profile.
PD Parameters	CD14/16 mononuclear cell counts, CSF-1, and biomarkers of kinase inhibition and myeloid cell recruitment. Surgical tissue will be evaluated for MGMT methylation, CSF-1, CSF1R, tumor-associated macrophages, and other prognostic biomarkers in order to correlate with treatment response and inform enrichment strategies for subsequent studies in this patient population. If the MGMT methylation status of the study population differs from that observed in the RTOG 0525 study, the benchmark mPFS of 5.5 months will be adjusted appropriately.
Endpoints	
Primary: Median PFS by RANO criteria
 
Secondary: Safety, OS, PK, correlative imaging
 
Exploratory: PD biomarkers

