**Table 2: PLX3397 Dosing Cohorts**

Cohort	Combination PLX3397/RT/TMZ		Adjuvant PLX3397/TMZ	
	PLX3397 Dose	PLX3397 Schedule	PLX3397 Dose	PLX3397 Schedule
-2	600 mg/day	5 days/week (M-F) b	800 mg/day b	7 days/week
-1	600 mg/day	7 days/week a	600 mg/day a 800 mg/day b	7 days/week
1	800 mg/day	7 days/week a 5 days/week (M-F) b	1000 mg/day b	7 days/week
2	1000 mg/day	5 days/week (M-F) b	1200 mg/day b	7 days/week

a Amendment 1.

b Amendment 2.

Study drug will be administered orally using a capsule formulation (200 mg per capsule). The total daily dose of PLX3397 will be divided and administered BID. For an uneven number of capsules, the larger dose will be administered in the morning.

For combination PLX3397/RT/TMZ PLX3397 treatment, dose escalation to the next highest cohort may occur after all patients have completed the 11-week DLT-observation period (i.e., 1-week PLX3397 monotherapy; 6-week PLX3397/RT/TMZ combination therapy; 4-week recovery). For adjuvant PLX3397/TMZ PLX3397 treatment, dose escalation to the next highest cohort may occur after all patients have completed an 8-week DLT-observation period (i.e.,

2 cycles of adjuvant treatment). For patients participating in Phase 1b, intra and inter patient dose escalation to a higher dose level/schedule will be permitted after that dose level/schedule has been established to be safe.

Prior to dose escalation, safety data will be collated and reviewed by the Sponsor and study sites by teleconference. A dose level will be considered unacceptable if 2 or more patients of the 6 eligible patients experience a DLT (see below). Should all 7 patients in the Cohort be analyzable for adverse events, only the first 6 will be considered in the determination of DLTs. A patient who misses more than 7 days of PLX3397 administration during the 7-week dosing period of Cycle 1 (4 weeks) and Cycle 2 (3 weeks) for reasons other than having had a DLT will be replaced. If 2 or more patients in a Cohort experience a DLT, no patients in the Cohort will be replaced.

If 2 or more of the first 6 patients in Cohort -2 (600 mg/day of PLX3397; 5 days/week [M-F]) experience a protocol-defined DLT, the combination will be considered too toxic and the study will be discontinued.

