### **13.16 Stopping Rules**

The Plexxikon Medical Monitor will monitor safety data throughout the course of the study. The Medical Monitor will review SAEs within timeframes mandated by company procedures and will review trends, laboratory analytes, and adverse events at periodic intervals and provide for interim safety analyses if appropriate. Safety data across all study patients will be reviewed at planned bimonthly teleconferences with all participating sites.

For Phase 1 dose escalation, a dose level will be considered unacceptable if 2 or more patients of the 6 eligible patients experience a DLT (see below). Should all 7 patients in the Cohort be analyzable for adverse events, only the first 6 will be considered in the determination of DLTs. A patient who misses more than 7 days of PLX3397 administration during the 7-week dosing period of Cycle 1 (4 weeks) and Cycle 2 (3 weeks) for reasons other than having had a DLT will be replaced. If 2 or more patients in a Cohort experience a DLT, no patients in the Cohort will be replaced.

If 2 or more of the first 6 patients in Cohort -2 (400 mg/day of PLX3397) experience a protocol-defined DLT, the combination will be considered too toxic and the study will be discontinued.

After approximately 50% of the planned Phase 2 patients have been completed their concurrent radiation therapy, an overall interim safety summary will be reviewed by the Medical Monitor and principal investigators to ensure that the potential clinical benefit outweighs the observed clinical risk to date. If the safety observations do not warrant continued enrollment, the study will be discontinued.

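### Exactly 2 DLTs in 6 patients is acceptable in Section 21.1.1 but unacceptable in Sections 6.0, 13.13.1 and 13.16, and the Cohort -2 study stop has three conflicting versions

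*Combined protocol and SAP*

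**What the plan says.** **Acceptability of a dose level.** Section 21.1.1 states: "A dose level for PLX3397 will be considered acceptable if no more than 2 patients of the 6 eligible patients experience a DLT". It continues: "If the current level is considered acceptable, then dose escalation will occur and the protocol will be reopened". If the level is not acceptable, the preceding acceptable level becomes the MTD.

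Three other sections state the rule the other way. In the synopsis (Section 6.0, Stopping Rules), "a dose level will be considered unacceptable if 2 or more patients of the 6 eligible patients experience a DLT". In Section 13.13.1, below Table 2: "A dose level will be considered unacceptable if 2 or more patients of the 6 eligible patients experience a DLT". In Section 13.16: "For Phase 1 dose escalation, a dose level will be considered unacceptable if 2 or more patients of the 6 eligible patients experience a DLT". All four sections count only the first 6 patients.

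**Study stop at the lowest level.** Section 6.0 discontinues the study on this condition: "If >2 of the first 6 patients in Dose Level -2 (400 mg/day of PLX3397) experience a protocol-defined DLT". Section 13.16 stops at 2 or more of the first 6 in Cohort -2, also described as 400 mg/day. Section 13.13.1 stops at 2 or more of the first 6 in Cohort -2, described as 600 mg/day on 5 days per week. Table 2 defines Cohort -2 as 600 mg/day, 5 days/week, in the combination period and has no 400 mg/day row. Section 10.2 still allows for a 400 mg cohort.

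**The concern.** In whole patients, acceptable at no more than 2 and unacceptable at 2 or more overlap at one count, exactly 2 of 6. That is the boundary of the decision rule. Identifying the recommended Phase 2 dose is the primary objective of Phase 1b (Section 9.0). The dose chosen is given to every Phase 2 patient, and the Phase 1 patients treated at it are pooled into the planned total of about 44 (Section 21.2). With 2 DLTs in 6, the statistical section sends new patients to a higher dose, while the other three sections declare the current dose too toxic.

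The Cohort -2 rule decides whether the whole study ends, so it needs one threshold and one dose. At exactly 2 of 6 in that cohort, Section 6.0 bars the dose without stopping the study, Section 13.13.1 stops the study, and Section 21.1.1 would escalate.

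**Working it through.** The documents state no operating characteristics for the DLT rule, so there is no figure of theirs to reproduce. The check has two steps.

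**1. The texts side by side**

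| DLTs in first 6 | Section 21.1.1 | Sections 6.0, 13.13.1, 13.16 |
|---|---|---|
| 0 or 1 | acceptable | not unacceptable |
| 2 | acceptable, escalate | unacceptable |
| 3 or more | not acceptable | unacceptable |

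| Study stop at the lowest level | Threshold | Dose named |
|---|---|---|
| Section 6.0 | more than 2 of 6 | 400 mg/day |
| Section 13.16 | 2 or more of 6 | 400 mg/day |
| Section 13.13.1 | 2 or more of 6 | 600 mg/day, 5 days/week |

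No two versions of the stop agree on both threshold and dose. Only Section 13.13.1 matches Table 2.

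**2. How often the conflict would matter**

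Inputs: n = 6 (Sections 6.0, 13.13.1, 13.16 and 21.1.1). The true DLT rate p is not in the documents and is assumed over 10% to 50%. With X ~ Binomial(6, p):

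- P(X = 2) = 15 p²(1 − p)⁴, the chance that the two rules disagree
- P(X ≤ 1) = (1 − p)⁶ + 6p(1 − p)⁵, the chance of acceptance under Sections 6.0, 13.13.1 and 13.16
- P(X ≤ 2) = P(X ≤ 1) + P(X = 2), the chance of acceptance under Section 21.1.1

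Example at p = 0.40: P(X ≤ 1) = 0.6⁶ + 6 × 0.4 × 0.6⁵ = 0.0467 + 0.1866 = 0.233. P(X = 2) = 15 × 0.16 × 0.1296 = 0.311. P(X ≤ 2) = 0.233 + 0.311 = 0.544.

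| Assumed p | P(exactly 2 of 6) | Accept if ≤ 1 | Accept if ≤ 2 |
|---|---|---|---|
| 0.10 | 0.098 | 0.886 | 0.984 |
| 0.20 | 0.246 | 0.655 | 0.901 |
| 0.33 | 0.329 | 0.358 | 0.687 |
| 0.40 | 0.311 | 0.233 | 0.544 |
| 0.50 | 0.234 | 0.109 | 0.344 |

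For the Cohort -2 stop, the chance of stopping is 1 − P(X ≤ 1) at 2 or more and 1 − P(X ≤ 2) at more than 2. That gives 0.345 against 0.099 at p = 0.20, and 0.767 against 0.456 at p = 0.40.

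**The case against.** The strongest reply is that the intended rule can be inferred. Three of four statements agree, including the operative escalation section and the dedicated stopping-rules section. Those three also say that no patient in a cohort is replaced once 2 or more have had a DLT, which makes sense only if 2 already decides the cohort. Section 21.1.1 looks like older text, since it speaks of two expected dose levels while Section 10.2 plans five cohorts. There is also a human check. Section 13.13.1 provides: "Prior to dose escalation, safety data will be collated and reviewed by the Sponsor and study sites by teleconference", and it says escalation may occur, not that it must. All of this stands, and it supports the direction of the correction. It does not remove the conflict: the review has to apply a threshold, and nothing says which one.

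Phase 1b may already have been finished under this version, which reschedules visits from 01 October 2017 and refers to the Phase 2 flow chart. The documents do not say so. If it was finished, rewording cannot change the dose, and the useful step is to report which rule was applied.

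The probabilities rest on assumed rates. Section 7.5 describes drug-related Grade 3 events as very uncommon. At an assumed 5%, P(exactly 2 of 6) = 15 × 0.05² × 0.95⁴ = 0.031, about 3%. Adding radiation and temozolomide could raise the rate, so the range above remains relevant.

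On the Cohort -2 stop, the greater-than sign in Section 6.0 could be a lost greater-than-or-equal sign. The synopsis keeps the two signs distinct elsewhere, so this is unlikely. If it were so, only the threshold difference would fall; the dose mismatch would remain. It is also fair that Cohort -2 is the lowest row of Table 2, so barring it leaves little room to continue in practice. Section 10.2 is worded as a contingency, but a 400 mg cohort below Cohort -2 cannot be reached if Section 13.13.1 stops the study there.

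**Conclusion.** The concern holds. Section 21.1.1 and the other three sections give opposite decisions at exactly 2 DLTs in 6. The conflict is in current text and is spelled out in words, so it does not depend on how a symbol was read. Over assumed DLT rates of 10% to 50%, a cohort lands on that count with probability 10% to 33%. At an assumed rate of 40%, the laxer rule more than doubles the chance of accepting the dose (0.544 / 0.233 = 2.3). These sizes depend on the assumed rates; the contradiction does not.

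The Cohort -2 stop is inconsistent in both threshold and dose, and Sections 6.0 and 13.16 attach it to a dose that Table 2 does not assign to that cohort. Pre-escalation review makes it less likely that the laxer rule is applied unnoticed, but it does not settle the rule. This should be corrected because it governs both the dose carried into Phase 2 and a study-level stop.

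**What to change.** - **Section 21.1.1:** make a dose level acceptable if no more than 1 of the 6 eligible patients has a DLT. This matches Sections 6.0, 13.13.1 and 13.16.
- **Sections 6.0 and 13.16:** set the study stop at 2 or more of the first 6 patients in Cohort -2, at 600 mg/day, 5 days/week. This matches Section 13.13.1 and Table 2.
- **Section 10.2:** delete the 400 mg reference. The 600 mg contingency in the same clause can go too, because Table 2 already includes 600 mg cohorts.
- **Study report:** if any cohort has already closed with exactly 2 DLTs in 6, state which rule was applied.

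The cost is wording in four sections, with no change in patients, visits or procedures. If this is treated as a significant change, Section 26.0 requires an amendment with the usual review and approval.
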